### **8.2.3.2 Safety Endpoints**

A description of safety measures is provided in Section 4.2.3.1.

The primary safety endpoints are AEs graded using CTCAE (Version 4.0) criteria. Safety will be assessed by quantifying the toxicities and grades experienced by subjects who have received MK-3475, including serious adverse events (SAEs) and events of clinical interest (ECIs). Immune-related ECIs, as described in Section 7.2.3.2 will be collected. Other safety endpoints include laboratory safety assessments, ECOG performance status, vital signs, 12-lead ECG and physical examinations.

### **8.2.4 Analysis Populations**

#### **8.2.4.1 Efficacy Analysis Populations**

The Full Analysis Set (FAS) population will serve as the primary population for the analysis of efficacy data in this study. The FAS population consists of all allocated subjects with subjects excluded for the following reasons:

- Failure to receive at least one dose of study treatment,
- Lack of baseline data for those analyses that require baseline data

Details on the approach to handling missing data are provided in Section 8.2.5 Statistical Methods.

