Treatment with MK-3475 will continue unless the subject meets the discontinuation criteria such as disease progression (evaluated by modified RECIST 1.1), unacceptable toxicity, or completion of 24 months of treatment with MK-3475 (refer to Section 5.8 for further details). Subjects who attain an investigator-determined confirmed CR may consider stopping trial treatment after receiving at least 24 weeks of treatment (Treatment Phase). Subjects who discontinue after at least 24 months of therapy for reasons other than disease progression or intolerance or who discontinue after attaining a CR may be eligible for up to one year of retreatment (Second Course Phase) after they have experienced radiographic disease progression. The decision to retreat will be at the discretion of the investigator only if no cancer treatment (including the treatment of marketed product of MK-3475) was administered since the last dose of MK-3475, the subject still meets the safety parameters listed in the Inclusion/Exclusion criteria and the trial remains open (refer to Section 7.1.5.2.1 for further details). After the end of treatment in Treatment Phase and Second Course phase, each subject will be followed for 30 days for adverse event monitoring (serious adverse events will be collected for 90 days after the end of treatment). Subjects who discontinue treatment for reasons other than disease progression will have post-treatment follow-up for disease status until initiating a non-study cancer treatment, disease progression, withdrawing consent, death, or the end of the study, whichever occurs first. Response and progression in the Second Course Phase will not count towards the ORR and PFS of the efficacy endpoint in

this trial. All subjects will be followed by telephone contact for overall survival until death, withdrawal of consent or the end of the study, whichever comes first. Clinical data may temporarily be locked to assess the efficacy endpoint, ORR per RECIST 1.1 for advanced melanoma when once all of the enrolled subject has either progression disease or has had an imaging 24 weeks after treatment initiation, whichever occurs first.

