### 8.2.5.1 Statistical Methods for Efficacy Analyses

For the primary efficacy endpoint centrally reviewed RECIST 1.1 response rate, the point estimate, 95% confidence interval, and p-value for testing the RECIST 1.1 response rate is greater than the historical control will be provided using exact binomial distribution. Subjects in the primary analysis population (FAS) without response data will be counted as non-responder.

Secondary efficacy evaluations of RECIST 1.1 response based on investigator assessment will also be conducted using the same methodology as for the primary efficacy analysis.

For PFS endpoint, Kaplan-Meier (KM) curves and median estimates from the KM curves will be provided as appropriate. Subjects without efficacy evaluation data or without survival data will be censored at Day 1. [Table 9](#) summarizes the key efficacy analyses.

Table 9 Analysis Strategy for Key Efficacy Variables

Endpoint/Variable ‡ (Description, Time Point)	Primary vs. Supportive Approach †	Statistical Method	Analysis Population	Missing Data Approach
Primary Hypothesis #1				
Overall RECIST 1.1 response by central radiology assessment	P	Exact test of binomial parameter	FAS	Subjects with missing data are considered non-responders
Secondary Hypothesis #1				
Overall RECIST 1.1 response rate based on site assessment	P	Exact methods for binomial parameter	FAS	Subjects with missing data are considered non-responders
Progression-free survival (RECIST 1.1)	P	Summary statistics using Kaplan-Meier method	FAS	Censored at last assessment
Response duration (RECIST 1.1)	P	Summary statistics using Kaplan-Meier method	All responders	Non-responders are excluded in analysis
Overall survival	P	Summary statistics using Kaplan-Meier method	FAS	Censored at last assessment
Overall irRC response rate based on central radiology review	P	Exact methods for binomial parameter	FAS	Subjects with missing data are considered non-responders
Progression-free survival (irRC)	P	Summary statistics using Kaplan-Meier method	FAS	Censored at last assessment
Response duration (irRC)	P	Summary statistics using Kaplan-Meier method	All responders	Non-responders are excluded in analysis

† P=Primary approach; S=Secondary approach.

The strategy to address multiplicity issues with regard to multiple efficacy endpoints is described in Section 8.2.6, Multiplicity and Section 8.2.9, Interim Analyses.

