### **8.2.6 Multiplicity**

The false positive rate for testing the primary efficacy endpoint is controlled at 0.025 (1-sided). No additional multiplicity adjustment is required.

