### **8.2.7 Sample Size and Power Calculations**

In this study, approximately total 35 subjects with advanced melanoma will be enrolled, among them at least 28 from cutaneous melanoma and at most 7 from mucosal melanoma. The 28 cutaneous melanoma subjects are the main analysis population. 7 subjects with mucosal melanoma are population for exploratory analysis.

With approximately 28 evaluable subjects with cutaneous melanoma, the study has approximately 90% power to detect a 25% difference in ORR under the null hypothesis of ORR=10% with a type I error rate of 2.5% if the true ORR is 35%. The null hypothesis rate of 10% is based on the historic response rate in large phase III trials for standard single agent chemotherapy in melanoma [21-30]. Success for this hypothesis requires at least 7/28 responses. The actual number of subjects enrolled may be larger than 28 to ensure that at least 28 subjects are evaluable for primary analysis.

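### The primary efficacy population is stated in two conflicting ways (an FAS with no melanoma-type restriction, or cutaneous subjects only), and the fixed count of 7 responses departs from the p<2.5% rule once 30 or more subjects are analysed

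*Combined protocol and SAP*

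**What the plan says.** Two sets of statements bear on who is in the primary test.

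**Text that uses the FAS.** Section 8.2.4.1 names the FAS as the primary efficacy population and says "The FAS population consists of all allocated subjects with subjects excluded for the following reasons": no dose received, or no baseline data where the analysis needs them. Section 8.1.1 defines the FAS differently (measurable disease at baseline, plus either a later scan or discontinuation for progression or a drug-related AE), again without reference to melanoma type. Section 8.2.5.1 says "Subjects in the primary analysis population (FAS) without response data will be counted as non-responder". Tables 8 and 9 list FAS for the primary test, and FAS or all responders for the secondary endpoints.

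**Text that uses cutaneous subjects.** The hypothesis in Section 3.1 and the secondary objectives in Section 3.2 concern cutaneous melanoma. Section 8.2.7 says "The 28 cutaneous melanoma subjects are the main analysis population", bases power on a calculation that begins "With approximately 28 evaluable subjects with cutaneous melanoma", and assigns mucosal subjects to exploratory analysis. Section 8.1.3 says the same. Section 8.2.8 calls cutaneous melanoma the main target population and gives mucosal subjects their own exploratory analysis.

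**Success rule.** Section 8.1.1 sets success at a one-sided exact p-value below 2.5%, and Section 8.2.6 controls the error rate at 0.025, one-sided. Sections 8.1.3 and 8.2.7 also state success as a count, at least 7 of 28, and Section 8.2.9 words it as more than 7 of 28. Sections 8.1.3 and 8.2.7 allow more than 28 to be enrolled so that at least 28 are evaluable.

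**The concern.** The sections that define analysis sets and assign them to endpoints do not carry the cutaneous restriction. No section defines a cutaneous FAS or says that Tables 8 and 9 apply to cutaneous subjects only. Section 8.2.8 adds a mucosal analysis, but does not take mucosal subjects out of the FAS. Someone programming from Section 8.2.4.1 and Table 9 would therefore analyse up to 35 subjects, and someone working from Section 8.2.7 about 28. Section 5.1.2 admits up to 7 mucosal subjects, so the two readings are likely to give different data sets.

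The trial is open-label with a single arm, and a positive result leads to a filing (Section 8.2.9). The denominator of its only confirmatory test should not be open to choice after responses are known. If the types were pooled, the error rate and power for the cutaneous hypothesis would also depend on the mucosal response rate, for which the plan gives no value.

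A second, separate issue is that the success count is fixed while the number of cutaneous subjects is not. Mucosal enrolment is only capped, so cutaneous n could lie anywhere from 28 to about 35.

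**Working it through.** **Inputs.** Null ORR 0.10, alternative 0.35, one-sided alpha 0.025, n=28 and success at 7 or more (Sections 8.2.6 and 8.2.7); about 35 enrolled, with at least 28 cutaneous and at most 7 mucosal (Section 8.2.7). Mucosal ORR is an assumption, varied from 0 to 30%.

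**Formula.** P(X ≥ k | n, p) = Σ from x=k to n of C(n,x) pˣ (1−p)ⁿ⁻ˣ.

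**1. The plan's own figure.** With n=28 and k=7, P(X ≥ 7 | 0.10) = 0.0179 and P(X ≥ 7 | 0.35) = 0.908. The stated 90% power and the 7/28 rule reproduce. Reading Section 8.2.9 literally as 8 or more of 28 gives alpha 0.0050 and power 0.818.

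**2. Literal FAS with 35 subjects, all at one ORR.**
- k=7: alpha 0.0552.
- k=8: alpha 0.0200, with power 0.958 if all 35 have ORR 35%.

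**3. Literal FAS with different ORRs.** Let X = Xc + Xm, with Xc ~ Bin(28, pc) and Xm ~ Bin(7, pm) independent. P(X ≥ 8) is the sum of P(Xc=i)·P(Xm=j) over i+j ≥ 8.

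| Mucosal ORR (assumed) | P(≥8/35), cutaneous ORR 10% | P(≥8/35), cutaneous ORR 35% |
|---|---|---|
| 0% | 0.005 | 0.818 |
| 5% | 0.011 | 0.847 |
| 10% | 0.020 | 0.873 |
| 15% | 0.033 | 0.896 |
| 20% | 0.050 | 0.915 |
| 30% | 0.101 | 0.946 |

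Of the values shown, the error probability for the cutaneous hypothesis is above 0.025 at mucosal ORR 15% and higher. Power is below the planned 0.908 at 15% and lower, and above it at 20% and higher.

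**4. Cutaneous subjects only, with n above 28.**

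| n | alpha with 7 responses | smallest count with p<0.025 | alpha at that count | power at that count (ORR 35%) |
|---|---|---|---|---|
| 28 | 0.0179 | 7 | 0.0179 | 0.908 |
| 29 | 0.0216 | 7 | 0.0216 | 0.926 |
| 30 | 0.0258 | 8 | 0.0078 | 0.876 |
| 32 | 0.0358 | 8 | 0.0117 | 0.918 |
| 35 | 0.0552 | 8 | 0.0200 | 0.958 |

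The critical value is 7 for n=25 to 29 and 8 for n=30 to 35. From n=30, 7 responses would satisfy a bare count but fail the p-value rule in Section 8.1.1.

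**The case against.** The best reply is that the plan does say who is in the primary analysis. Sections 8.1.3 and 8.2.7 name the cutaneous subjects as the main analysis population, Section 8.2.8 agrees, and Section 8.2.2 brings the Section 3.0 hypotheses into the SAP. The FAS rule can then be read as governing dosing and baseline data, with histology settled elsewhere. This shows what was intended, and it stands to that extent. It does not remove the conflict, because Section 8.2.5.1 equates the primary analysis population with the FAS, and the tables repeat FAS without qualification.

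It is also fair to say that 7/28 carries its own denominator, that nothing in the plan states 7/35, and that Section 8.1.1 already has a p-value rule that adapts to n. These points stand. They show that the p-value rule should govern, but the plan does not say that it overrides the counts in Sections 8.1.3, 8.2.7 and 8.2.9.

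A mucosal ORR above the cutaneous ORR may be thought unlikely, since Section 4.2.3.2 describes mucosal melanoma as having a poor prognosis. The plan gives no mucosal rate, so the whole assumed range is shown, including the part where pooling does not inflate error and the part where it does not cost power.

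A reader might also infer pooling from the data-lock text in Section 2.1, which refers to "ORR per RECIST 1.1 for advanced melanoma". That sentence sets the timing of a possible lock for all enrolled subjects. It does not define an analysis population and is not relied on here.

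**Conclusion.** The plan contains two conflicting definitions of the primary efficacy population, and the conflict reaches the secondary efficacy endpoints as well. It should be settled before the main analysis.

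A reader might go further and conclude that mucosal subjects do enter the primary test, or that the 7-response threshold and the sample size are wrong. The documents do not support that: mucosal subjects are expressly exploratory, and the threshold and power are right for 28 cutaneous subjects.

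The size of the problem depends on the reading. If the FAS were applied literally to 35 subjects, a count of 7 would give alpha 0.0552 with every subject at ORR 10%. With the correct count of 8, the chance of success at cutaneous ORR 10% would be 0.005 to 0.101, and power at cutaneous ORR 35% would be 0.818 to 0.946, for mucosal ORR 0 to 30%. These ranges assume 28 cutaneous and 7 mucosal subjects with independent responses, and the mucosal rates are assumptions.

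The fixed-count problem does not depend on pooling. On the cutaneous-only reading, a count of 7 exceeds 0.025 from n=30 (0.0258) and reaches 0.0552 at n=35.

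**What to change.** - In Sections 8.1.1 and 8.2.4.1 and in Tables 8 and 9, state that the primary and secondary efficacy analyses use subjects with cutaneous melanoma within the FAS. Keep the separate mucosal analysis already planned in Section 8.2.8. Use one FAS definition in both sections while the text is open.
- In Sections 8.1.3, 8.2.7 and 8.2.9, state that success is an exact one-sided p<0.025 in that population, with critical value 7 for n=25 to 29 and 8 for n=30 to 35 cutaneous subjects. This also removes the difference between at least 7 and more than 7.

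The cost is SAP wording only. Sample size, enrolment and trial conduct do not change. One consequence should be recorded: because the critical value steps up at n=30, power there is 0.876, a little below the planned 90%.

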#### **8.2.4.2 Safety Analysis Populations**

The All Patients as Treated (APaT) population will be used for the analysis of safety data in this study. The APaT population consists of all allocated subjects who received at least one dose of study treatment.

At least one laboratory, 12-lead ECG or vital sign measurement obtained subsequent to at least one dose of study treatment is required for inclusion in the analysis of each specific parameter. To assess change from baseline, a baseline measurement is also required.

Details on the approach to handling missing data for safety analyses are provided in Section 8.2.5 Statistical Methods.

### **8.2.5 Statistical Methods**

Statistical testing and inference for safety analyses are described in 8.2.5.2. Efficacy results that will be considered to be statistically significant after consideration of the strategy for controlling the Type I error are described in Section 8.2.6, Multiplicity. Unless otherwise stated, all statistical tests will be conducted at the  $\alpha=0.05$  (2-sided) level.

### 8.2.5.1 Statistical Methods for Efficacy Analyses

For the primary efficacy endpoint centrally reviewed RECIST 1.1 response rate, the point estimate, 95% confidence interval, and p-value for testing the RECIST 1.1 response rate is greater than the historical control will be provided using exact binomial distribution. Subjects in the primary analysis population (FAS) without response data will be counted as non-responder.

Secondary efficacy evaluations of RECIST 1.1 response based on investigator assessment will also be conducted using the same methodology as for the primary efficacy analysis.

For PFS endpoint, Kaplan-Meier (KM) curves and median estimates from the KM curves will be provided as appropriate. Subjects without efficacy evaluation data or without survival data will be censored at Day 1. [Table 9](#) summarizes the key efficacy analyses.

Table 9 Analysis Strategy for Key Efficacy Variables

Endpoint/Variable ‡ (Description, Time Point)	Primary vs. Supportive Approach †	Statistical Method	Analysis Population	Missing Data Approach
Primary Hypothesis #1				
Overall RECIST 1.1 response by central radiology assessment	P	Exact test of binomial parameter	FAS	Subjects with missing data are considered non-responders
Secondary Hypothesis #1				
Overall RECIST 1.1 response rate based on site assessment	P	Exact methods for binomial parameter	FAS	Subjects with missing data are considered non-responders
Progression-free survival (RECIST 1.1)	P	Summary statistics using Kaplan-Meier method	FAS	Censored at last assessment
Response duration (RECIST 1.1)	P	Summary statistics using Kaplan-Meier method	All responders	Non-responders are excluded in analysis
Overall survival	P	Summary statistics using Kaplan-Meier method	FAS	Censored at last assessment
Overall irRC response rate based on central radiology review	P	Exact methods for binomial parameter	FAS	Subjects with missing data are considered non-responders
Progression-free survival (irRC)	P	Summary statistics using Kaplan-Meier method	FAS	Censored at last assessment
Response duration (irRC)	P	Summary statistics using Kaplan-Meier method	All responders	Non-responders are excluded in analysis

† P=Primary approach; S=Secondary approach.

The strategy to address multiplicity issues with regard to multiple efficacy endpoints is described in Section 8.2.6, Multiplicity and Section 8.2.9, Interim Analyses.

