##### **5.1.2 Subject Inclusion Criteria**

In order to be eligible for participation in this trial, the subject must:

1. Be willing and able to provide written informed consent for the trial. The subject may also provide consent for Future Biomedical Research. However, the subject may participate in the main trial without participating in Future Biomedical Research.
2. Be  $\geq$  20 years of age on day of signing informed consent.

3. Have histologically confirmed diagnosis of locally advanced (unresectable Stage III) or metastatic (Stage IV) melanoma not amenable to local therapy.
  - Subject may not have a diagnosis of uveal or ocular melanoma.
  - Subject who have mucosal melanoma are eligible.

NOTE: the proportion of subjects with mucosal melanoma will not exceed 20% of the total subjects (limited up to 7 subjects).

  - Subject who have received 0-2 prior lines of therapy (excluding adjuvant or neoadjuvant therapy) for melanoma.
  - LDH  $\leq$  local ULN
4. Have at least one measurable lesion as defined by RECIST 1.1 on imaging studies (CT or MRI).

Note: Tumor lesions situated in a previously irradiated area are considered measurable if progression has been demonstrated in such lesions.

Note: Cutaneous lesions and other superficial lesions are not considered measurable lesions for the purposes of this protocol, but may be considered as non-target lesions.
5. Have a performance status of 0 or 1 on the ECOG Performance Scale.
6. Have an anticipated life expectancy of at least 3 months.
7. Demonstrate adequate organ function as defined in [Table 1](#), all screening labs should be performed within 10 days of treatment initiation.

Table 1 Adequate Organ Function Laboratory Values

System	Laboratory Value
Hematological	
Absolute neutrophil count (ANC)	$\geq 1,500 / \text{mcL}$ (without supportive care)
Platelets	$\geq 100,000 / \text{mcL}$
Hemoglobin	$\geq 9 \text{ g/dL}$ or $\geq 5.6 \text{ mmol/L}$ (without transfusions)
Renal	
Serum creatinine OR Measured or calculated creatinine clearance (CrCl) a (GFR can also be used in place of creatinine or CrCl)	$\leq 1.5 \times$ upper limit of normal (ULN) OR $\geq 50 \text{ mL/min}$ for subjects with creatinine levels $> 1.5 \times$ institutional ULN
Hepatic	
Serum total bilirubin	$\leq 1.5 \times$ ULN (or $< 3 \times$ ULN in subjects with Gilbert's syndrome) OR direct bilirubin $\leq$ ULN for subjects with total bilirubin levels $> 1.5 \times$ ULN

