### **7.1.3.4 Tumor Imaging and Assessment of Disease**

The tumor imaging (CT or MRI) for screening should be performed within 4 weeks prior to the first dose of trial treatment. The site study team must review pre-trial images to confirm the subject has measurable disease per RECIST 1.1. The baseline imaging scan should be submitted to the central imaging vendor for a retrospective analysis of this eligibility criterion. Scans performed as part of routine clinical management are acceptable for use as the screening scan if they are of diagnostic quality and performed within 4 weeks prior to the first dose of trial treatment. The same imaging technique should be used in a subject throughout the study.

Tumor imaging should be performed every 6 calendar weeks ( $\pm$  1 week) starting at 12 weeks through 48 weeks, and after 48 weeks, imaging assessments should be performed every 12 calendar weeks ( $\pm$  1 week) (i.e. Screening visit, Cycles 5, 7, 9, 11, 13, 15, 17 and then every 4 cycles [12 weeks]) or more frequently if clinically indicated. Tumor imaging timing should follow calendar days and should not be adjusted for delays in cycle starts or extension of MK-3475 cycle frequencies. Tumor response will be assessed using irRC (See Section 12.6) and the RECIST 1.1 criteria (See Section 12.5) by the central independent radiology review.

After the first documentation of progression per RECIST 1.1, it is at the discretion of the investigator to keep a clinically stable subject on trial treatment or to stop trial treatment until at least 4 weeks later confirms progression or scheduled next confirmatory scan (6 or 12 weeks later from the first documentation of progression). When feasible, subjects should not be discontinued until progression is confirmed per modified RECIST 1.1 criteria, in which a confirmation assessment of disease progression must be obtained at least 4 weeks after the initial disease assessment indicating progressive disease as discussed below in [Table 6](#). Clinically stable is defined by the following criteria:

- Absence of signs and symptoms indicating disease progression
- No decline in ECOG performance status
- Absence of rapid progression of disease
- Absence of progressive tumor at critical anatomical sites (e.g., cord compression) requiring urgent alternative medical intervention

Table 6 Imaging and Treatment after 1st radiologic evidence of PD

	Clinically Stable		Clinically Unstable	
	Imaging	Treatment	Imaging	Treatment

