## **8.0 STATISTICAL ANALYSIS PLAN**

### **8.1 Statistical Analysis Plan Summary**

This section contains a brief summary of the statistical analyses for this trial. Full detail is in the Statistical Analysis Plan (SAP) (Section 8.2).

The primary purpose of this study is to investigate the safety, tolerability, and anti-tumor activity of MK-3475 administered intravenously to subjects with advanced melanoma.

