#### **8.1.1 Efficacy Analyses**

The full analysis set (FAS) population (defined as all subjects with a baseline scan with measurable disease and who either have a post baseline scan or discontinue the trial due to progressive disease or a drug-related AE) will serve as the primary population for the analyses of efficacy data in this trial. Overall response rate based on RECIST 1.1 will be used as the primary endpoint for efficacy assessment. A 95% confidence interval along with a one-sided p-value for testing the null hypothesis (ORR=10%) based on the binomial distribution will be provided for the response rate. The study is considered to have reached the efficacy objective if the corresponding p-value for testing the respective null hypothesis is less than 2.5%. An outline of the efficacy analysis strategy is presented in [Table 8](#) below.

Table 8 Primary Analysis Strategy for Efficacy Endpoints

Endpoint/Variable (Description, Time Point)	Statistical Method	Analysis Population	Missing Data Approach
Primary:			
Overall RECIST 1.1 response rate based on central radiology review	Exact test of binomial parameter	FAS	Subjects with missing data are considered non-responders
Secondary:			
Overall RECIST 1.1 response rate based on site assessment	Exact methods for binomial parameter	FAS	Subjects with missing data are considered non-responders
Progression-free survival (RECIST 1.1)	Summary statistics using Kaplan-Meier method	FAS	Censored at last assessment
Response duration (RECIST 1.1)	Summary statistics using Kaplan-Meier method	All responders	Non-responders are excluded in analysis
Overall survival	Summary statistics using Kaplan-Meier method	FAS	Censored at last assessment
Overall irRC response rate based on central radiology review	Exact methods for binomial parameter	FAS	Subjects with missing data are considered non-responders
Progression-free survival (irRC)	Summary statistics using Kaplan-Meier method	FAS	Censored at last assessment
Response duration (irRC)	Summary statistics using Kaplan-Meier method	All responders	Non-responders are excluded in analysis

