### **8.2.3 Analysis Endpoints**

#### **8.2.3.1 Efficacy/Immunogenicity/Pharmacokinetics Endpoints**

Efficacy and safety endpoints that will be evaluated for are listed below, followed by the descriptions of the derivations of selected endpoints.

The primary efficacy endpoint is response rate, defined as the proportion of subjects in the analysis population who have complete response (CR) or partial response (PR) using RECIST 1.1 criteria at any time during the study. Response for the primary analysis will be determined by the central independent radiology review.

Key secondary efficacy endpoints include:

- Response rate based on site assessments using RECIST 1.1

Other secondary efficacy endpoints include: (1) duration of response, defined as time from first RECIST 1.1 response to disease progression in subjects who achieve a PR or better; (2) progression-free survival (PFS), defined as the time from allocation to the first documented disease progression according to RECIST 1.1 or death due to any cause, whichever occurs first; (3) overall survival (OS) ; (4) Response rate based on irRC ; (5) duration of response based on irRC and (6) progression-free survival (PFS) based on irRC.

Immunogenicity/pharmacokinetics endpoints are exploratory endpoints in this study. Immunogenicity endpoint include anti-MK-3475 antibody and pharmacokinetics endpoints include pharmacokinetic parameters of MK-3475.

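### Read literally, the Day 1 censoring sentence for PFS censors a treated subject who dies before any post-baseline scan, although the SAP counts that death as a PFS event (minor)

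*Combined protocol and SAP*

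**What the plan says.** Section 8.2.3.1 defines PFS as time from allocation to "the first documented disease progression according to RECIST 1.1 or death due to any cause, whichever occurs first". No scan or follow-up contact is needed for a death to count.

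Section 8.2.5.1, in its PFS paragraph, says: "Subjects without efficacy evaluation data or without survival data will be censored at Day 1". The two conditions are joined by *or*, no exception is made for a recorded event, and the term for efficacy data is not defined. Tables 8 and 9 give a different rule for missing PFS data, censoring at the last assessment, and do not say how the two rules fit together.

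Section 7.1.3.4 schedules on-study imaging every 6 weeks "starting at 12 weeks through 48 weeks", "or more frequently if clinically indicated".

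The FAS in Section 8.2.4.1 drops subjects for "Failure to receive at least one dose of study treatment" or for missing baseline data that an analysis needs. A treated early death therefore stays in. The summary FAS in Section 8.1.1 is narrower. It keeps subjects with measurable disease at baseline "who either have a post baseline scan or discontinue the trial due to progressive disease or a drug-related AE".

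**The concern.** A treated subject who dies in week 8 without an unscheduled scan has a PFS event under Section 8.2.3.1. The same subject has no post-baseline tumour data, so the literal Day 1 rule removes that subject from the risk set at the start. Two programmers following the SAP could code this death differently.

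The subjects affected are the earliest failures. Censoring them at Day 1 makes PFS look better from the death onward, and this single-arm trial has no control arm to share the error. Section 8.2.9 plans to prepare for filing on the main analysis, so the rule should be unambiguous before the data are seen.

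**Working it through.** **The plan's own figure.** The documents project nothing for PFS. The only design figure is the ORR power in Section 8.2.7: n = 28, null 10%, alternative 35%, success at 7 or more responses. The exact binomial gives P(X ≥ 7 | 10%) = 0.0179 and P(X ≥ 7 | 35%) = 0.908, which reproduces the stated power of approximately 90%. The Day 1 sentence does not enter this calculation.

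**Effect from the death onward.** Take 28 cutaneous subjects, of whom d die unscanned before any other event, with no other early censoring.
- Deaths counted: S(t) = [(28-d)/28] × (product of later steps, starting from 28-d at risk).
- Deaths censored at Day 1: S(t) = the same product without the first factor.
- Ratio: 28/(28-d).

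Just before week 12, for d = 1, the estimate is 27/28 = 96.4% if the death is counted and 100% if it is censored, a gap of 3.6 points. Where the true value is 50%, the literal rule gives:
- d = 1: 0.5 × 28/27 = 51.9%
- d = 2: 0.5 × 28/26 = 53.8%

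With an assumed 8 progressions at week 12, PFS at that scan is:
- d = 1: 19/28 = 67.9% counted, 19/27 = 70.4% censored
- d = 2: 18/28 = 64.3% counted, 18/26 = 69.2% censored

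**Effect before the death.** Suppose one subject progresses on an unscheduled week-4 scan and another dies unscanned at week 8.
- Weeks 4 to 8: 27/28 = 96.4% counted, 26/27 = 96.3% censored, so slightly lower.
- After week 8: 26/28 = 92.9% counted, 26/27 = 96.3% censored, so higher.

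If a subject misses every scan and dies at week 30, with 8 progressions at week 12, week-12 PFS is 20/28 = 71.4% counted and 19/27 = 70.4% censored. The overstatement starts only at the death.

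**Precision.** At 50%, the standard error is √(0.25/28) = 9.4 points.

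**How often it could happen.** The documents give no early-death rate for this trial. Section 4.1.1 reports more than approximately 80% alive at one year in another MK-3475 study. Assume 80% and a constant hazard:
- Death before day 84: 1 - 0.80^(84/365.25) = 0.050, or 1.4 of 28.
- With a share f of those deaths unscanned, P(at least one) = 1 - (1 - 0.050f)^28.

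| Assumed f | P(at least one), 80% alive at one year | P(at least one), 90% (assumed) | Mean shift at a true 50%, 80% case |
|---|---|---|---|
| 1 | 76% | 49% | 2.7 points |
| 0.5 | 51% | 29% | 1.3 points |
| 0.25 | 30% | 15% | 0.7 points |

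The 80% column is probably high. Entry requires LDH at or below the upper limit of normal, ECOG 0 or 1, and "Have an anticipated life expectancy of at least 3 months".

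**Median.** For d = 1, the 50% mark falls at the 13th of the other 27 subjects if the death is counted and at the 14th if it is censored. The median moves only if those two progress at different scans. With simulated exponential PFS on the imaging schedule (8,000 trials), it is unchanged in 82% of trials at an assumed median of 12 weeks and in 52% at 36 weeks.

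**The case against.** A censoring rule ordinarily applies to subjects without an event, and nothing in Section 8.2.5.1 says that it displaces the definition in Section 8.2.3.1. That section lists OS and death-inclusive PFS among the efficacy endpoints, so a recorded death could itself count as efficacy data. Read as covering subjects with neither type of data, the sentence conflicts with nothing. This objection stands in part. A reader might infer that the SAP plainly orders recorded events to be overridden; the documents support only that its literal wording does so and that no passage excludes that reading.

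The condition on missing survival data has the same flaw on paper: a documented progression without survival data would be censored at Day 1. A reader might infer that progressions would be lost in numbers. That is not supported, because a scan showing progression also shows the subject alive that day, and all subjects are followed by telephone for survival (Section 1.0), until withdrawal of consent or the end of the study at the latest. The condition should rarely matter, and no size is claimed for it.

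A reader might also infer that Day 1 censoring can only raise the curve. It cannot be put that way: it also shrinks the risk set for events before the death, so the curve is marginally lower until then.

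Finally, the choice of FAS decides whether some of these subjects enter the analysis at all. That is true, but it does not remove the problem. A subject who discontinued for progressive disease or a drug-related AE and then died unscanned satisfies the post-baseline part of the narrower Section 8.1.1 definition too. The mismatch between the two definitions should be reconciled as a separate matter.

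**Conclusion.** The point holds as a minor wording defect. A stated rule, read literally, gives the wrong status to a treated subject who dies before any post-baseline tumour assessment, and nothing else in the SAP settles the reading.

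One or two such deaths among 28 would overstate a true 50% by 1.9 or 3.8 points from the deaths onward, well inside a standard error of 9.4 points. The 28/(28-d) factor assumes no other event before the deaths and no other early censoring. The frequency and median figures rest on assumed survival, an assumed share of unscanned deaths and assumed median PFS, none of which the documents give for this trial.

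PFS is summarised descriptively and not tested. A reader might infer a threat to the efficacy claim, but the Day 1 sentence plays no part in the primary ORR test, its type I error or its power.

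**What to change.** Replace the Day 1 sentence in Section 8.2.5.1 with: *Any documented progression or death is a PFS event on its date, whichever occurs first; only subjects with no post-baseline tumour assessment and no recorded death are censored at Day 1.* All other event-free subjects remain censored at their last assessment, as Tables 8 and 9 already provide. Also state whether the same death rule applies to irRC PFS, which Section 8.2.3.1 names without defining.

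The cost is one reworded sentence and one clarification. No new data are needed, because survival follow-up is already planned for all subjects. The downside is that PFS estimates may come out slightly less favourable.
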